3.2 General study level definitions

3.2.1 Relative day

The relative day will be included in different listings and will be calculated as follows:

- If the start (stop) date occurred on or after the first dose, but prior to the double-blind drug stop date, relative day is calculated as start (stop) date minus first dose date + 1
- If the start (stop) date occurred after the last dose of double-blind drug, the relative day to the most recent dose is calculated as start (stop) date minus most recent dose date. The relative day in this situation will be preceded by a ‘+’
- If the start (stop) date occurred before the first dose, the relative day is calculated as start (stop) date minus first dose date. The relative day in this situation will be preceded by a ‘-’.

For AEs, relative days for start and stop dates will be calculated as the number of days since the first injection of the medication. For non-treatment emergent AEs, relative day of onset will be negative if the event started and stopped before the first dose. Relative day will only be computed for fully completed dates and will be missing for partial dates.

Relative day will be calculated from first dose of IMP for all treatment groups, and additionally from first dose of bimekizumab for the Placebo/BKZ 320mg Q2W arm.

3.2.2 Mapping of data from Premature End of Treatment visits

If the Premature end of treatment (PEOT) visit occurs at a scheduled visit as outlined in the schedule of assessments, then no mapping is necessary, and any early withdrawal assessments will correspond to that scheduled visit. The PEOT assessments that occur on a date after a scheduled visit will be assigned to the next scheduled site visit per the protocol following the last visit where assessments were available. This approach means that there is a chance that data will be mapped to a visit where a given assessment was not actually collected per the protocol schedule of assessments. Such data will not be summarized in by-visit tables (though it will be available in the listings).

The only exception to the above rule is for anti-bimekizumab antibody assessments, in which all PEOT assessments will be assigned to the next scheduled visit at which anti-bimekizumab antibodies are assessed. All by-visit summaries will contain nominal visits only. Unscheduled visits will not be mapped to scheduled visits. Note that based on the early withdrawal mapping conventions described above, a mapped PEOT visit is considered as observed at that visit and will be summarized as such in the tables.

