Per protocol, visit windows are ± 3 days from the date of first dose. The 20-week SFU Visit window is ± 7 days from the date of the final dose. All-by-visit summaries will contain nominal (ie, scheduled) visits only. Unscheduled visits will not be mapped to scheduled visits except for assessments that occur within a 3-day time window of a scheduled visit. In that case, the assessment will be mapped to the corresponding scheduled visit and will be used for the analysis. This will only occur for selected vendor data. The only exception to this rule is for unscheduled assessments that occur up to 3 days after the Baseline visit. These unscheduled visits will remain as unscheduled as the Baseline assessment cannot be after the first dose of study drug administration. See Section 3.3 for more details on the definition of Baseline values.

A complete set of data listings containing all documented data as well as calculated data (eg, change from Baseline) will be generated.

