- **Treatment policy strategy:** All available data observed at the time point of interest will be considered, regardless of the occurrence of intercurrent events. This means the analysis includes on- and off-treatment values collected after study participants prematurely discontinued study treatment but agreed to remain on the study and continued to attend visits and provide assessments at those visits as well as values from study participants who received rescue antibiotic medication. Those observed values will be analyzed according to the study participant’s randomized treatment. Study participants for whom efficacy data cannot be obtained at the week of interest, despite attempts to retain them in the study, will have their data imputed using MI – MCMC / monotone.

The following table depicts which missing data handling approaches will be used based on endpoint priority (primary, secondary, other) and endpoint type (responder, continuous, ordinal).

Table 4–1: Missing data handling approach by endpoint priority and type

End-point Priority	Endpoint Type	Composite Estimand (NRI)	Modified Composite Estimand (MI)	MI (MCMC/Reference -based)	Tipping Point	Treatment Policy	Hypothetical Estimand	OC
Primary	Responder	S ^a	P	S ^a	S	S ^a		S
Secondary included in the statistical testing procedure	Responder	S ^a	P					S
	Continuous						P	S
Secondary not included in statistical testing procedure	Binary	X	X					X
	Continuous						X	X
Other	Responder	X ^d	X					X ^d
	Continuous						X	X ^b
	Ordinal						X ^c	X ^c

MI=multiple imputation, NRI=Nonresponder imputation, OC=Observed case, P=Primary method, S=Sensitivity method, X=Method to be used (no priority designated).

Note: Composite estimand (NRI) refers to the approach in which data preceded by the intercurrent event of study treatment discontinuation due to AE or lack of efficacy or receipt of rescue antibiotic medication are imputed as nonresponse, and other missing data are also imputed as nonresponse.

Note: Modified Composite Estimand (MI) refers to the approach in which data preceded by the intercurrent event of study treatment discontinuation due to AE or lack of efficacy or receipt of rescue antibiotic medication are imputed as nonresponse, and other missing data are imputed via a multiple imputation model.

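### Premature end-of-treatment assessments are placed by the last attended visit rather than by their own date, so after two or more missed visits a value is back-dated by at least two weeks and counted as observed

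*SAP*

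**What the plan says.** Section 3.2.2 separates two cases. If the PEOT visit falls at a scheduled visit, "then no mapping is necessary, and any early withdrawal assessments will correspond to that scheduled visit". Otherwise, "The PEOT assessments that occur on a date after a scheduled visit" are each placed at a scheduled visit that is found from the attendance record: the assessment "will be assigned to the next scheduled site visit per the protocol following the last visit where assessments were available".

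The section then fixes the status of the result: "a mapped PEOT visit is considered as observed at that visit and will be summarized as such in the tables".

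Two limits are stated. An assessment mapped to a visit where it is not scheduled is listed but left out of the by-visit tables. And "The only exception to the above rule is for anti-bimekizumab antibody assessments", which go to the next visit at which those antibodies are measured.

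Section 3.1 gives the general tolerance: "Per protocol, visit windows are ± 3 days from the date of first dose". Its 3-day limit on mapping is written for unscheduled assessments (and selected vendor data only). It is not applied to PEOT data.

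**The concern.** The rule does what it should only when the participant attended every visit up to the PEOT. The next visit after the last attended one is then also the next visit after the PEOT date. Once visits have been missed the two separate, and the rule follows the attendance record instead of the calendar. A value measured late is stored under an earlier week, with no cap on the distance, and from then on is handled like an assessment made on time.

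Three places are exposed:

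- **Primary and binary secondary endpoints.** Under Sections 3.9 and 4.2.1.1, stopping treatment for a reason other than an adverse event or lack of efficacy is not an intercurrent event. A missing Week 16 value in such a participant is multiply imputed from the visit history (Section 4.2.2.1). A back-dated value either replaces that imputation at Week 16 or enters the history at the wrong week.
- **Treatment-policy sensitivity analysis (Section 8.2.3.4).** It uses all available values regardless of intercurrent events, so it takes the mapped values as they are.
- **By-visit tables** of assessments that are scheduled at the assigned visit.

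**Working it through.** The plan states no figure here, so the check is to apply the rule as written.

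**Inputs**
- Anchor: last visit with available assessments (Section 3.2.2). This could mean any assessment or the assessment in question. Neither reading lets the PEOT date choose the visit.
- Visit spacing: 2 weeks. This is an assumption, taken from dosing every 2 weeks from Week 0 to Week 46 (Section 7). The schedule of assessments is not in the SAP.
- Visit window: ±3 days (Section 3.1).
- Intercurrent-event date after stopping for an adverse event or lack of efficacy: last dose + 17 days (Section 3.9).

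**Formula.** Let L be the week of the last visit with data and k the number of consecutive visits missed before the PEOT.
- PEOT date: between week L + 2k and week L + 2k + 2.
- Assigned visit: week L + 2.
- Shift = PEOT date − assigned visit: between 2k − 2 and 2k weeks, that is 14k − 14 to 14k days.

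| Missed visits k | Shift in days | Effect |
|---|---|---|
| 0 | −14 to 0 | carried forward |
| 1 | 0 to 14 | back-dated |
| 2 | 14 to 28 | back-dated |
| 3 | 28 to 42 | back-dated |

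Each further missed visit adds 14 days.

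**Case A: the value lands on the primary time point.** Last data at Week 14, Weeks 16 and 18 missed, PEOT at Week 19. Assigned visit: 14 + 2 = Week 16. Shift: 19 − 16 = 3 weeks = 21 days, against a window of 3 days. The Week 19 count is stored as an observed Week 16 count.

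**Case B: the value is moved away from the primary time point.** Last data at Week 10, Weeks 12 and 14 missed, PEOT at Week 15.5. Assigned visit: 10 + 2 = Week 12. Shift: 15.5 − 12 = 3.5 weeks. The value lies half a week from Week 16 but is filed at Week 12, and Week 16 is left to imputation.

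**Does the composite strategy remove this?** For most participants with an intercurrent event, yes. An event before Week 16 sets response to failure at that and all later visits, whatever was observed. One edge is unsettled. If the last dose was at Week 14 (day 98 after first dose), the event date is 98 + 17 = day 115, which is 3 days after the Week 16 target (day 112). A PEOT value filed at Week 16 then precedes the event if the mapped visit date is compared, and follows it if the actual date is compared. The SAP does not say which date is used.

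**The case against.** The strongest reply is that the pattern is rare and its reach short. With no missed visit, the current rule and a date-based rule give the same visit. With one missed visit the shift stays under two weeks. A shift of two weeks or more needs at least two consecutive missed visits followed by attendance at a PEOT visit. Antibiotic rescue, and stopping for an adverse event or lack of efficacy, already fix nonresponse for the binary endpoints. Time to response and time to flare use actual dates (Sections 8.4.1.2 and 8.4.5). Some mapped values never reach a table, because the assessment is not scheduled at the assigned visit. All of this stands. It limits the effect but does not repair the rule.

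Two stronger readings are tempting and are not supported.

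- **A large loss of information in the Week 16 imputation.** A reader might infer this by assuming a visit-to-visit correlation and a long run of missed visits. The SAP gives neither a correlation nor a count of affected participants, and a long run of missed visits is the extreme case. No effect on a response rate, an odds ratio or the type I error, and no direction between arms, can be derived.
- **Two records competing for one visit.** Section 4.2.1.4 does foresee participants who "prematurely discontinued study treatment but agreed to remain on the study and continued to attend visits", so a reader might infer that a PEOT and a real visit collide. Section 3.2.2 is written for early withdrawals, however. Whether participants who stay in the study have a separate PEOT between scheduled visits depends on a schedule that the SAP does not show.

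**Conclusion.** The point holds in a limited form. The rule in Section 3.2.2 ignores the PEOT's own date, sets no maximum gap and labels the result as observed, and nothing elsewhere in the SAP corrects this. On a 2-week grid, two or more consecutive missed visits back-date the value by at least two weeks, and a Week 19 value can become the Week 16 endpoint. Wider spacing of site visits would give larger shifts.

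Those affected are participants with missed visits before PEOT. For the primary endpoint they are mainly those stopping for reasons other than an adverse event or lack of efficacy. Their number is unknown and probably small, so this is a defect worth correcting and not a threat to the trial's main conclusion.

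**What to change.** Replace the anchor in Section 3.2.2 with the PEOT date, in this order:

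1. Assign the PEOT assessment to the scheduled visit whose ±3-day window contains it, if that visit has no assessment of its own.
2. Otherwise assign it to the next scheduled visit after the PEOT date, if that visit has no assessment of its own.
3. Otherwise keep it as unscheduled.
4. Leave missed visits in between missing.

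The window check has to come first. Without it, a PEOT one day after the target day of a missed visit would be pushed forward 13 days although it lies inside that visit's window. The own-assessment condition also settles any collision, should one occur.

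Under this rule Case A goes to Week 20 and Week 16 stays missing, to be imputed. Case B goes to Week 16, carried forward by half a week.

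The cost is a few sentences in the SAP and a change to the mapping program, best made before unblinding. The remaining drawback is that a PEOT up to just under two weeks before a visit is still carried forward to it, as already happens under the current rule when no visit is missed.

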3.3 Definition of Baseline values

Section 8.3.3 details the derivation of the Baseline value for the HSSDD assessment. For all other assessments, the below applies.

A Baseline value for a participant is defined as the latest non-missing measurement for that participant up to and including the day of administration of first study medication, unless otherwise stated. If a Baseline assessment is taken on the same day as first administration of study medication, it is eligible to be used as the Baseline value, even in the case that the time of the assessment is recorded as taking place after the time of first study medication administration. This is considered acceptable as this measurement is still the best representation of the Baseline value of the given assessment since it is highly unlikely that the study medication could have an impact on any measurement in such a short period of time. However, such cases should be rare as study center personnel are instructed to do all assessments at the Baseline visit prior to administering study medication. One exception to this rule is plasma concentration of bimekizumab. If Baseline plasma concentration is measured at a time after the first administration of study medication, then it will not be eligible to be considered as a Baseline plasma concentration. Such cases will be discussed with the quantitative clinical pharmacologist.

For randomized participants for whom no start date of treatment is available, the Baseline value will be considered as the last available value on or before the randomization date.

If a Baseline measurement is missing or not collected, and a Screening value is available, the Screening value will be utilized as Baseline instead.

Baseline values for component scores should be computed using components from the same visit where the relevant measurements were recorded prior to dosing. For example, if the Screening visit has all of the components, but the Baseline visit is missing 1 or more components, the Baseline value for the component score should be calculated using the Screening visit values.

When the time of first dose is derived, it will be based on the first injection of study treatment, regardless of whether or not it is an active treatment.

3.4 Protocol deviations

Important protocol deviations are deviations from the protocol that could potentially have a meaningful impact on study conduct or on the primary and key secondary efficacy, key safety, or PK outcomes for an individual participant. The criteria for identifying important protocol deviations will be defined within the appropriate protocol-specific document at study start. Important protocol deviations will be reviewed as part of the ongoing data cleaning process. Important protocol deviations including those that lead to exclusion from the analysis sets will be identified and documented prior to unblinding.

Deviations related to the Coronavirus Disease 2019 (COVID-19) global pandemic are unavoidable deviations from the protocol due to confirmed COVID-19 infection, suspected COVID-19 infection, general circumstances around COVID-19 without infection or any other deviation from the protocol due to COVID-19. COVID-19 protocol deviations will also be reviewed separately as part of the ongoing data cleaning process.

3.5 Analysis sets

3.5.1 Enrolled Set

The Enrolled Set (ES) will consist of all participants who have given informed consent.

3.5.2 Randomized Set

The Randomized Set (RS) will consist of all participants randomized into the study.

3.5.3 Safety Set

The Safety Set (SS) will consist of all participants who received at least 1 dose (full or partial) of IMP. The SS will be used for the demographic, safety, and immunogenicity analyses.

3.5.4 Full Analysis Set

The Full Analysis Set (FAS) will consist of all study participants who received at least 1 dose (full or partial) of IMP and had a valid Baseline measurement and a post-Baseline measurement for abscess, inflammatory nodules, and draining tunnel counts.

3.5.5 Active Medication Set

The Active Medication Set (AMS) will consist of all participants who have received at least 1 dose (full or partial) of bimekizumab. The AMS will be used for summaries of safety that include all data from the Initial Treatment Period and/or Maintenance Treatment Period.

3.5.6 Maintenance Set

The Maintenance Set (MS) will consist of all participants who have received at least 1 dose (full or partial) of bimekizumab in the Maintenance Treatment Period.

3.5.7 Per-Protocol Set

The Per-Protocol Set (PPS) will consist of all study participants in the FAS who had no important protocol deviations affecting the primary efficacy variable. Important protocol

deviations will be predefined and study participants with important protocol deviations will be evaluated during ongoing data cleaning meetings prior to unblinding of the data.

3.5.8 Pharmacokinetics Per-Protocol Set

The Pharmacokinetics Per-Protocol Set (PK-PPS) will consist of study participants who received at least 1 full dose of bimekizumab and provided at least 1 quantifiable plasma concentration post-dose without important protocol deviations that would affect the PK.

3.5.9 COVID-19 Free Set

The COVID-19 Free Set (CFS) will consist of all study participants randomized into the study and who have no COVID-19 impact through Week 16. This analysis set will be used for sensitivity analysis of the primary efficacy endpoint.

3.6 Treatment assignment and treatment groups

It is expected that participants receive treatment as randomized and hence safety analyses will be based on the SS, as randomized. However, if after unblinding it is determined that participants randomized to placebo in the Initial Treatment Period received bimekizumab at any time within the first 16 weeks, then for safety analyses these participants will be reallocated to the appropriate bimekizumab treatment group, unless otherwise specified. Participants randomized to bimekizumab will only be reallocated to the placebo treatment group if they never received bimekizumab. Efficacy analyses will be according to randomized treatment and not actual treatment received.

For the purposes of Initial Treatment Period analyses for the 320mg Q2W dosing regimen, the bimekizumab treatment arms of 320mg Q2W/Q2W and bimekizumab 320mg Q2W/Q4W treatment groups will be pooled.

3.7 Center pooling strategy

Geographic regions have been categorized as North America, Western Europe, Central/Eastern Europe, and Asia/Australia. Below is a table of geographic regions with corresponding countries.

Table 3-1: Geographic regions and corresponding countries

Region	Countries
North America	Canada, United States
Western Europe	Belgium, France, Germany, Italy, Norway, Spain, Switzerland, Denmark, Netherlands
Central/Eastern Europe	Greece
Asia/Australia	Australia, Israel, Turkey

The following center pooling algorithm will be used for each geographic region:

- If a center has 21 or more participants, then no pooling will be done for that center.
- Centers with fewer than 21 participants will be ordered from largest to smallest with pooling proceeding in the following manner:
 - Two or more centers will be combined until the cumulative participant total is at least 21.

- Once a pooled center has at least 21 participants, the process will continue in an iterative fashion for the subsequent centers in the ordered list, where a new pooled center begins each time at least 21 participants has been reached in the previous pool.
- If this iterative process reaches the end of the ordered list of centers where the final pooled center has fewer than 21 participants, then the participants from the centers in that pool will be combined with the pooled center formed in the previous iteration.

This procedure is only to be performed within a geographic region – there will be no pooling of centers across regions.

In the event that the percentage of randomized participants is less than 10% in either of the Asia/Australia or Central/Eastern Europe regions, the two regions will be combined as a geographic region stratum for efficacy modeling, so that there are no modeling convergence issues across efficacy variables.

3.8 Coding dictionaries

Adverse events and medical history will be coded using the Medical Dictionary for Regulatory Activities (MedDRA®) version 19.0.

Medications will be coded according to the World Health Organization Drug Dictionary (WHODD) version MAR2021 B3 or later. Medical procedures will not be coded.

3.9 Definition of an intercurrent event

Handling of intercurrent events is one of the key elements for the analysis of efficacy endpoints.

An intercurrent event is defined as receipt of systemic antibiotic rescue medication or discontinuation of study treatment due to an AE or lack of efficacy (See Section 8.2.2).

Receipt of systemic antibiotic rescue medication is defined as initiating any systemic antibiotic on or after Baseline for any reason (including in response to an AE). The only exception to this rule is if a participant randomized to the antibiotic stratum on a tetracycline antibiotic interrupts their stable dose of tetracycline antibiotic during the study and subsequently restarts the same tetracycline antibiotic as confirmed using the coded preferred term. The restarted dose and frequency of the antibiotic must be the same or lower than the regimen prior to the interruption.

The dates of an intercurrent event are as follows:

- For receipt of systemic antibiotic rescue medication: start date of the antibiotic
- For discontinuation of study treatment due to an AE or lack of efficacy: Last study treatment date + 17 days. Note: study treatment discontinuation includes study discontinuation.

The choice of 17 days is intended to capture the interval between dosing and lesion assessments (14 days), as well as the visit window (3 days).

An additional sensitivity analysis will be conducted where missing data due to COVID-19 will be considered an intercurrent event and will be imputed as a nonresponse at that particular visit. This will be identified when there are missing data at a visit that has been impacted by COVID-19 according the COVID-19 impact CRF page. The date of this intercurrent event will be the date of the impacted visit.

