4.2.3.1 Composite estimand

A composite estimand strategy as defined in Section 8.2.2 allows incorporation of the two intercurrent events (eg, receipt of systemic antibiotic rescue medication or discontinuation of study treatment due to an AE or lack of efficacy) within the definition of the endpoint. These intercurrent events are considered meaningful to the efficacy outcome following receipt of study medication. For example, within the proposed composite estimand framework, a randomized study participant who discontinues from study treatment due to lack of efficacy prior to Week 16 will be considered a treatment failure at Week 16 regardless of the lesion count assessment performed at that visit.

The assumptions and robustness of the primary analysis (modified composite estimand as defined in Section 8.2.2) will be assessed through the sensitivity analyses defined in Section 8.2.3. The impact of intercurrent event handling and data imputation methods on endpoint derivation will also be assessed via the analyses of lesion counts and derived HiSCR variables as specified in Section 8.4.2.1 and Section 8.4.1.1, respectively.

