7 MEASUREMENTS OF TREATMENT COMPLIANCE

Due to the method of administration of the treatments, compliance will be examined in terms of completed injections.

Treatment compliance will be calculated as:

$$\frac{N_{actual}}{N_{expected}} \times 100\%$$

where N_{actual} is the total number of actual (completed) injections, and $N_{expected}$ is the total number of expected injections. In this study, dosing occurs every 2 weeks from Week 0 to Week 46, where 2 injections are administered at each given visit either with active dosing or placebo injection. It is expected that a participant should complete a total of 48 injections by the end of study. If a participant discontinues early, then the number of expected injections is based on the time of early discontinuation relative to the dosing visits. For example, if a participant discontinues after Week 8 visit and prior to Week 10 visit, the total number of expected injections will be 10.

A summary of percent treatment compliance categorized as <75% and $\geq 75\%$ will be provided by treatment group for each study period (Initial Treatment Period for the RS, Maintenance Treatment Period for the MS, and the combined Initial and Maintenance Treatment Period for the AMS).

A by-participant listing of treatment compliance will be provided.

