8.2.2 Primary analysis of the primary efficacy endpoint

The primary endpoint is the HiSCR₅₀ response at Week 16 and corresponding analyses are based on the RS. The primary efficacy analysis will evaluate the composite estimand in the RS as described in Table 8-1. The composite estimand combines the clinically meaningful improvement from Baseline based on the HiSCR₅₀ response and completion of study treatment through Week 16 without receiving systemic antibiotic rescue medication or discontinuing IMP due to an AE or lack of efficacy.

The following 4 attributes describe the estimand that will be used to define the treatment effect of interest for the primary efficacy analysis:

1. Population=Study participants meeting the protocol-specified inclusion/exclusion criteria.
2. Study participant-level outcome=HiSCR₅₀ at Week 16.
3. Intercurrent event handling=An intercurrent event is defined as receipt of systemic antibiotic rescue medication or discontinuation of study treatment due to an AE or lack of efficacy prior to Week 16. More information is provided in Section 3.9. A composite strategy will be implemented in which a positive clinical outcome is defined as achieving HiSCR₅₀ at Week 16 and not receiving systemic antibiotic rescue medication, and not discontinuing study treatment due to an AE or lack of efficacy through Week 16. Any missing data at Week 16 that are not preceded by an intercurrent event will be imputed using multiple imputation as defined in Section 4.2.1. The rationale for this composite estimand is provided in Section 4.2.3.1.

4. Population-level summary measure=conditional odds ratio comparing bimekizumab to placebo adjusted for stratification factors used in the randomization.

The statistical hypothesis for the HiSCR₅₀ response at Week 16 is that the conditional odds ratio for the HiSCR₅₀ response in the bimekizumab treatment group relative to the placebo group is equal to 1.

The primary analysis will be based on a logistic regression model including a fixed effect for treatment, Hurley stage at Baseline, and Baseline antibiotic use. The odds ratio versus placebo, p-value (from Wald test), and 97.5% CI will be calculated. If one dose regimen is tested at the 0.05 significance level as determined in Section 4.5, then the confidence interval will be 95% instead of 97.5% for that dose with a corresponding $Z_{\alpha/2}$ of 1.96.

The number and percentage of participants who are HiSCR₅₀ responders at Week 16 will be summarized.

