10.1.1.2 Time at risk (days)

Definitions for time at risk (days) are provided as follows:

- For participants who complete the Week 16 visit and continue to the Maintenance Treatment Period:
 - Date of first dose in the Maintenance Treatment Period – Date of first dose in the Initial Period + 1.
- For participants who discontinue on or prior to the final visit of the Initial Period, use the minimum of the following:
 - Date of last dose in the Initial Treatment Period – Date of first dose in the Initial Treatment Period + 141
 - The total number of days in the Initial Treatment Period (112 days). For AEs that emerged after 112 days but still within the 140 days window, those AEs would be

classified as TEAE, but will be excluded from the output based on the Initial Treatment Period. However, these AEs will be included in the AE summaries for Maintenance Treatment Period.

- Date of last clinical contact – Date of first dose in the Initial Treatment Period + 1.
- For participants who die prior to the final visit of the Initial Treatment Period: Date of death – date of first dose in the Initial Period +1.

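### Dating an AE or lack-of-efficacy discontinuation at last dose + 17 days generally places a stop after an on-time or late Week 14 dose after the Week 16 visit, contrary to the composite estimand

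*SAP*

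**What the plan says.** Section 3.9 gives the dating rule, "For discontinuation of study treatment due to an AE or lack of efficacy: Last study treatment date + 17 days", and its reason: "17 days is intended to capture the interval between dosing and lesion assessments (14 days), as well as the visit window (3 days"). Section 4.2.1.1 then sets the primary variable to nonresponse at the timepoint of the event and at every later one, but not before.

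The estimand text is framed by the discontinuation itself. Section 4.2.3.1 gives the example of a participant "who discontinues from study treatment due to lack of efficacy prior to Week 16 will be considered a treatment failure at Week 16", whatever the lesion count shows. Section 8.2.2 defines a positive outcome as requiring no AE or lack-of-efficacy discontinuation up to and including Week 16.

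Two further rules decide what happens when the event does not come first. Section 8.2.2: "Any missing data at Week 16 that are not preceded by an intercurrent event will be imputed using multiple imputation". Section 3.2.2 assigns a PEOT assessment made after a scheduled visit to the next scheduled site visit, and "a mapped PEOT visit is considered as observed at that visit".

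**The concern.** A participant who takes the Week 14 dose and then stops for an AE or lack of efficacy before Week 16 is a failure under Sections 4.2.3.1 and 8.2.2. Under Sections 3.9 and 4.2.1.1, read as a comparison of dates, that participant usually has no intercurrent event by Week 16. Two routes to a score the estimand does not intend then open:

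- **Missing Week 16.** The value goes to multiple imputation under missing at random, so a known AE or lack-of-efficacy dropout may be imputed as a responder. Imputation runs separately by treatment group (Section 4.2.2.1), so a bimekizumab dropout is imputed from bimekizumab data, although conditional on that participant's earlier lesion counts.
- **PEOT assessment between Weeks 14 and 16.** It is mapped to Week 16, treated as observed, and may count as a response.

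No passage says which text governs, so the programmer would have to choose for the primary endpoint. HiSCR75 and skin pain response inherit the question through Section 4.2.1.2.

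**Working it through.** **Inputs (SAP), counting days from first dose = day 0**

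- Dosing: "dosing occurs every 2 weeks from Week 0 to Week 46" (Section 7), with active or placebo injections at each visit. Week 14 is nominally day 98 (14 × 7).
- Week 16: "The total number of days in the Initial Treatment Period (112 days") (Section 10.1.1.2), so nominally day 112.
- Window: "visit windows are ± 3 days from the date of first dose" (Section 3.1). The Week 14 dose falls on days 95 to 101 and the Week 16 visit on days 109 to 115.

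**The plan's figure.** 14 + 3 = 17 days, as stated.

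**Event date.** Event day = Week 14 dose day + 17. The event counts at Week 16 if it falls on or before the visit day.

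| Week 14 dose day | Event day | In-window visit days on or after the event | Count of 7 |
|---|---|---|---|
| 95 | 112 | 112 to 115 | 4 |
| 96 | 113 | 113 to 115 | 3 |
| 97 | 114 | 114, 115 | 2 |
| 98 (on time) | 115 | 115 | 1 |
| 99 | 116 | none | 0 |
| 100 | 117 | none | 0 |
| 101 | 118 | none | 0 |

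Total: 4 + 3 + 2 + 1 = 10 of 49 combinations are scored as events, and 49 − 10 = 39 are not. With an on-time or late dose, 1 of 28 is scored and 27 are not. These are counts of calendar possibilities, not probabilities.

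**Earlier last doses.** A last dose at Week 12 (days 81 to 87) gives an event on days 98 to 104, always before day 109. Only stops after the Week 14 dose are affected at the primary timepoint.

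**Missing Week 16.** There is no visit date to compare. Against nominal day 112, only a dose on day 95 gives an event in time. Against the window end, day 115, on-time and early doses do, but late doses (events on days 116 to 118) still do not.

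**Mapped PEOT.** If its own date is used, any PEOT assessment made fewer than 17 days after the last dose precedes the event. If it is treated as a Week 16 visit, the table applies.

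**Scale of one participant.** 1/70 = 1.4 percentage points on placebo; 1/140 = 0.7 on Q4W; 1/280 = 0.4 on pooled Q2W.

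**The case against.** The 17 days are a deliberate and explained choice. They keep a lesion count taken about 14 days after the last dose as an on-treatment value, and for an attended Week 16 visit that is reasonable. This stands. The reason does not reach a participant who has no Week 16 assessment, or only an earlier PEOT assessment.

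Timepoint in Section 4.2.1.1 could also mean the windowed visit. An event on the last window day would then fall at Week 16 and be scored. That is a fair reading and would cover the on-time dose, but not doses given 1 to 3 days late.

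The nonresponder-imputation sensitivity analysis (Section 8.2.3.1) sets every missing Week 16 value to nonresponse, and the worst-case tipping-point scenario does so for bimekizumab. That limits the missing-data route. It leaves the PEOT route open, because a mapped PEOT value is not missing. The observed-case analysis as worded in Section 8.2.3.5 relies on the same event date and may keep such values, although the general definition in Section 4.2.1.4 would drop someone who has discontinued treatment.

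A reader might infer more than the documents support:

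- That every stop after Week 14 escapes. Doses on days 95 to 97 place the event inside the window, and an event on the visit day counts.
- That these participants become responders. Not being forced to nonresponse leaves the lesion counts, observed or imputed, to decide, and they may still show nonresponse.
- That every by-visit responder table lags by one visit. That needs a lesion assessment about 14 days after each person's last dose, and the assessment schedule is not in the SAP.

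**Conclusion.** The point holds as a conflict between the dating rule and the plan's own primary estimand. After an on-time or late Week 14 dose, the derived date is Week 16 + 3 days or later and generally does not precede the Week 16 visit. The same participant may then be imputed under missing at random or counted from a mapped PEOT assessment, although the estimand text calls that participant a nonresponder. This rests on reading Sections 3.9 and 4.2.1.1 as a comparison of dates; the SAP does not say that Sections 4.2.3.1 and 8.2.2 override it.

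The effect is probably small. It concerns only the last of the eight dosing intervals before Week 16, and within it only participants whose Week 16 value is missing or PEOT-derived, plus attended visits if the estimand wording is meant to override them. The SAP gives no rate of AE or lack-of-efficacy discontinuation, so the number affected and the net shift between arms cannot be derived. It is worth correcting because it touches the primary analysis and the correction is cheap.

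**What to change.** 1. In Section 3.9, add for the binary endpoints: if a participant discontinued for an AE or lack of efficacy before the scheduled visit, and the value at that visit is missing or comes only from a mapped PEOT assessment, the intercurrent event is taken to precede that visit and the value is nonresponse. For continuous endpoints, a PEOT-mapped value in this situation is set to missing and imputed.
2. Reconcile Sections 3.9, 4.2.3.1 and 8.2.2 by stating whether an attended, scheduled Week 16 assessment within last dose + 17 days counts as observed or is overridden. Item 1 alone leaves this open, and two participants stopping on the same day for the same reason could be scored differently by attendance.
3. Use one boundary, on or before the visit, throughout. Section 8.2.2 now refers both to events before Week 16 and to events through Week 16, while Section 8.2.3.5 uses on or before.

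The cost is SAP wording and one programming condition, settled before unblinding. Response rates may come out very slightly lower.
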